We propose that if sufficient doses of commonly employed analgesics are administered to humans, otherwise appropriate cardiovascular responses to the hemorrhagic insult will be suppressed, thereby reducing the ability of the individual to tolerate that insult. That said, the effects of analgesic doses of such agents (i.e., doses that are recommended for the pre-hospital setting) on physiological responses necessary to preserve tolerance to a hemorrhagic insult in humans is entirely unknown. Thus, the objective of this work is to identify the effects of sublingual sufentanil on tolerance to a simulated hemorrhagic challenge in humans.

STU-2021-0579

[figure not shown]
[figure not shown]
b. Current practice

A 30 microgram dose of sufentanil (trade name: Dsuvia) is administered sublingually for the management of acute pain.

3. Study Design.

Describe the study design (e.g., single/double blind, parallel, crossover, etc.) Consider inserting a scheme to visually present the study design.

We will conduct a double-blind, placebo-controlled, crossover study. Following informed consent and screening, eligible participants will be randomized to complete the sufentanil or the placebo trial first, with the other “agent” administered during the subsequent visit. During these experimental visits, we will administer two assessments of pain perception (described in greater detail below), then administer sufentanil sublingually or a placebo pill also sublingually, perform the simulate hemorrhagic tolerance assessment (lower-body negative pressure), and then re-assess the measures of pain perception. The graphics below depicts the study design and experimental protocol, respectively.

**EXPERIMENTAL PROTOCOL****4. Research Plan / Description of the Research Methods:****4.a. Provide a comprehensive narrative describing the research methods.**

- 1) Provide the order in which tests/procedures will be performed,
- 2) Provide the setting for these events and a description of the methods used to protect privacy during the study.
- 3) Provide the plan for data analysis (include as applicable the sample size calculation)

Please respond to all components of this item, or clearly indicate which components are not applicable.

Inclusion:

- 18-45 years of age
- Healthy
- Body mass index less than 33 kg/m²
- Body mass greater than or equal to 60 kg
- Speak English

Exclusion:

- Subjects not in the defined age range

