The setting for all visits will be the Institute for Exercise and Environmental Medicine. Trials will be conducted in controlled laboratory settings. During the experimental visits (sufentanil and placebo), we will record baseline cardiovascular measures. UT-Southwestern anesthesiologist [name], or a research nurse (with direct oversight from [name]) will administer sufentanil (30 microgram tablet) or placebo tablet during each experimental visit (i.e., participants will receive only one 30 microgram tablet of sufentanil). We will assess brachial blood pressure, nervous system activity via ultrasound-guided microneurography from the upper arm, beat-to-beat arterial blood pressure via photoplethysmography, cerebral perfusion via transcranial Doppler, limb blood flow via Doppler ultrasound, heart rate via electrocardiogram, respiration rate and end-tidal CO₂ via capnography from a nasal cannula, peripheral oxygen saturation via pulse oximetry, compensatory reserve via photoplethysmography, and plasma catecholamine concentrations from serial blood samples collected throughout the visit (~4 tablespoons per experimental visit). In addition, both before and after sufentanil/placebo administration, pain perception will be accessed via a cold pressor test (2-3

Form A

STU-2021-0579

minutes of a hand placed in a water/ice slurry) and via a pressure algometer assessment (pressure applied to the hand to the point of discomfort).

Data analysis will be performed as done previously in [name] laboratory in companion studies addressing the same questions but with ketamine (STU 092017-068), fentanyl (STU 092017-069), and morphine (STU 092017-070). Specifically, we will compare cardiovascular data (inclusive of nervous system activity data) between time points (baseline and post-drug/placebo administration) and conditions. We will also assess tolerance to the simulated hemorrhage challenge between sufentanil and placebo trials. All data will be analyzed while blind to condition and with proper co-variate analysis

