Personal health information (PHI) that is collected will be kept in a key-lock filing cabinet in a key-lock room only accessible to study team members within a numeric-padlocked laboratory. As described in the eIRB portal, a coded number system will be used in place of the participants name to de-identify their research information collected. A participant ID key, only accessible to study team members, will link the participants 'information with the coded number. Additionally, we follow all applicable University of Texas Southwestern IRB and Institute of Exercise and Environmental Medicine (i.e., where the research will take place) guidelines for protecting research participant privacy.

Up to 60 participants are anticipated to enroll in this study. No study has evaluated the effects of sufentanil on lower-body negative pressure (LBNP) tolerance in humans. The power and sample size estimates are based on findings from [name] laboratory showing reduced LBNP tolerance in the heat-stressed individuals. In that study heat stressed reduced LBNP tolerance by ~70% ($P<0.001$). Though we expect sufentanil to likewise reduce LBNP tolerance, we do not anticipate as large of a reduction as that observed with heat stress. The power analysis was calculated using G*Power [Ttests – Means: Difference between two dependent means (matched pairs)] using an estimated reduction in the cumulative stress index to sufentanil of 25% relative to LBNP tolerance of a normothermic subjects taking a placebo (i.e., placebo: 988 ± 402 units; sufentanil: 741 ± 300 units). These predictions resulted in an effect size of 0.68. Having a correlation of 0.5, with a study power=0.80 at an adjusted alpha=0.05, yielded an estimated subject size of 15 individuals. That value was inflated to 30 subjects (15 male and 15 female) to permit a comparison in the primary responses within sexes. Given the potential for subject dropouts, we propose to recruit up to 60 individuals to obtain complete datasets from 30 subjects. Since the effects of sufentanil on LBNP tolerance has never been assessed, the indicated values are estimates and thus interim power analyses will be performed, with the number of required subjects adjusted based upon the variance of the obtained data.

4.b. List of the study intervention(s) being tested or evaluated under this protocol

	N/A - this study does not test or evaluate an intervention. Skip to item 4.d.		

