When the participant is undergoing any testing, they will be supervised by an ACLS trained nurse and/or physician. Of note, a board-certified anesthesiologist will always be present when sufentanil is administered. There is a fully stocked “crash cart” with a defibrillator and medications (including naloxone) within 50 feet of the laboratory. IV anti-arrhythmic medications are rapidly available if a sustained but not life-threatening arrhythmia were to occur. Airway management equipment is also stocked in that cart. Furthermore, the Texas Health Resource Emergency Room is minutes away if an escalation of care is required.

Upon screening, participants will be given contact information for a nurse to contact in case any adverse event occurs following discharge from experimental days. However, this is unlikely to occur given the short-acting effects of sufentanil and the fact that participants are not discharged until vital signs are similar to that of baseline values.

c. Will the safeguards be different between/among groups?

Yes

No

Statistical Analysis

Data was assessed for normality and are presented as means \pm SD or medians [interquartile ranges], when appropriate. Based on our prior data investigating pharmacologic agents' effects on tolerance to LBNP (12, 24, 25), a sample size of $n = 15$ was estimated, but to maintain consistency with the previous studies, we recruited 29 individuals. Paired t-tests or Wilcoxon Signed-Rank tests were used for all paired comparisons (e.g., Urine-specific gravity, CSI, pain ratings, differences in CSI between the sexes etc.). Plasma catecholamine concentrations were compared between trials (placebo vs. sufentanil) using mixed-effects model analyses. Cardiovascular and cerebrovascular responses were evaluated every 30 seconds for the cold pressor test [time x trial], and the last minute of each LBNP stage [LBNP stage x trial], with the variables with each challenge compared using repeated-measures two-way ANOVAs or mixed-effects model. If a significant interaction was identified, a post hoc Šidák multiple comparison test was employed. A < 0.05 was considered statistically significant. Data were analyzed using GraphPad Prism 9 (GraphPad Software Inc., La Jolla, CA, USA).

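### The Statistical Analysis section puts the between-sex CSI comparison under paired tests, although men and women are independent groups

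*Combined protocol and SAP*

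**What the plan says.** - Statistical Analysis, on the tests: paired t-tests or Wilcoxon signed-rank tests were "used for all paired comparisons (e.g., Urine-specific gravity, CSI, pain ratings, differences in CSI between the sexes etc". The sex item is listed separately from CSI itself, so it is not simply the main drug-versus-placebo test.
- Section 3 (Study Design) gives the source of pairing: "We will conduct a double-blind, placebo-controlled, crossover study", in which "eligible participants will be randomized to complete the sufentanil or the placebo trial first". Each participant is his or her own control.
- Section 4.a, data analysis: "We will also assess tolerance to the simulated hemorrhage challenge between sufentanil and placebo trials".
- Section 4.a, sample size: the power calculation is for a "Difference between two dependent means (matched pairs"). It gives 15 participants, and then: "That value was inflated to 30 subjects (15 male and 15 female) to permit a comparison in the primary responses within sexes".
- Statistical Analysis, on numbers: "to maintain consistency with the previous studies, we recruited 29 individuals".

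The only interactions named in the Statistical Analysis section are time by trial and LBNP stage by trial. Neither part of the document names a two-sample t-test, a Mann-Whitney test or a trial-by-sex term. The split of the 29 by sex is not given.

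**The concern.** A paired test needs a defined link between the two members of each pair. Here that link exists between one person's placebo and sufentanil visits, but not between a man and a woman. The sentence can be read in two main ways.

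- **Reading A, literal.** Men are tested against women with a paired test. This requires an arbitrary male-female pairing, and it leaves participants out if the sexes are unequal in number.
- **Reading B, following section 4.a.** Placebo is compared with sufentanil separately in men and in women. Paired tests are valid for each sex's drug effect, but they do not test a difference between the sexes, which is what the Statistical Analysis section names.

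Section 4.a gives the sex comparison as the reason for going from 15 to 30 participants, so it is not an incidental analysis. Under A, the reported p-value would depend on a choice that the plan does not define. Under B, no between-sex test exists, and a significant result in one sex beside a non-significant one in the other could be misread as a sex difference.

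**Working it through.** **Inputs.** From section 4.a: placebo CSI 988 ± 402, sufentanil CSI 741 ± 300, correlation 0.5, power 0.80, alpha 0.05, n = 15. From Statistical Analysis: 29 recruited, significance level 0.05. Assumptions: the same SD of the within-person difference in both sexes; a 15/14 split, with others shown; two-sided tests unless stated.

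**Step 1. Reproduce the plan's own figure.**
- SD of the within-person difference = √(402² + 300² − 2 × 0.5 × 402 × 300) = √131,004 = 361.9.
- Effect size = (988 − 741)/361.9 = 247/361.9 = 0.68, as stated.
- By the noncentral t distribution, a paired test with n = 15 has power 0.807 one-sided, which reproduces the plan's 15, and 0.69 two-sided. This calculation covers only the within-person drug effect.

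**Step 2. Reading A: forced pairs against an unpaired test.** The quantity compared is each person's placebo-minus-sufentanil CSI difference (SD 361.9). The true sex difference is set at 247 units, as large as the whole planned drug effect.
- Unpaired: standard error = 361.9 × √(1/n₁ + 1/n₂), with n₁ + n₂ − 2 df.
- Forced pairs: m = the smaller group, SD of a pair difference = 361.9 × √2, with m − 1 df.

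| Men/women (either way round) | Unpaired df | Unpaired power | Forced pairs | Paired df | Paired power |
|---|---|---|---|---|---|
| 15/14 | 27 | 0.43 | 14 | 13 | 0.39 |
| 14/14 | 26 | 0.41 | 14 | 13 | 0.39 |
| 17/12 | 27 | 0.42 | 12 | 11 | 0.33 |
| 19/10 | 27 | 0.39 | 10 | 9 | 0.28 |

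Dependence on the pairing was simulated with 1000 datasets per scenario, normal differences with SD 361.9, and 300 random pairings of each dataset.
- With a true 247-unit sex difference at 15/14, the paired p-value fell on both sides of 0.05 in 63% of datasets (47% using only the central 95% of pairings).
- At 14/14 the figures were 51% and 38%.
- With no true difference at 15/14, a single random pairing rejected in 5.2% of datasets, against 4.9% for Welch.

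**Step 3. Reading B: one test per sex.** Suppose that both sexes truly have the planned 247-unit effect.
- Power is 0.691 with n = 15 and 0.656 with n = 14.
- Probability that exactly one sex is significant = 0.691 × (1 − 0.656) + (1 − 0.691) × 0.656 = 0.44.
- At 19/10 the powers are 0.803 and 0.487, and the probability is 0.51.
- At 15/14 it is 0.50 for a correlation of 0.3 and 0.25 for a correlation of 0.7.
- With one-sided tests at 0.05 (powers 0.807 and 0.780) it is 0.807 × 0.220 + 0.193 × 0.780 = 0.33.

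**Step 4. What a correct unpaired test can show at 15/14.**
- Expected 95% CI half-width = t(0.975, 27) × 361.9 × √(1/15 + 1/14) = 2.052 × 134.5 = 276 units.
- Difference detectable with 80% power = 391 units, or 391/247 = 1.58 times the planned drug effect.

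**The case against.** The best defence is that the sentence covers only paired comparisons, that section 4.a speaks of comparisons within sexes, and that its power calculation is for matched pairs. Together these favour reading B, under which the named test is valid and the fault lies in two or three words. The protocol's objective does not require a test of sex difference, and no text draws a between-sex conclusion from separate p-values. That reading is plausible, but the Statistical Analysis section does say between the sexes, so the text still names a comparison that its test does not make.

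A second defence is that a loose list swept in an item that was in fact analysed with an unpaired test. The documents cannot exclude this. The result would then stand, but the stated test would still be wrong and the one used unreported.

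Several limits on the size are fair. No document describes a male-female pairing, and 29 people cannot form complete pairs, so reading A may never have been carried out. The larger power losses need splits that the documents do not give. The discordance figure under B depends on sidedness, which the plan does not state. The CI width and detectable difference in Step 4 are limits of the sample size, and correcting the sentence will not change them.

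**Conclusion.** The concern holds. As written, a paired test is assigned to a comparison of two independent groups, and no test in the plan fits that comparison. Confidence is high on this mismatch; which analysis was actually run cannot be told from the documents.

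The consequences are moderate. Under a forced pairing, false positives are not inflated and the power loss is small for near-equal groups; the more serious fault is a p-value that the plan does not determine. Under within-sex testing, the fault is a missing between-sex test and the risk of over-reading a split result. These figures rest on the planning SDs and correlation applying to both sexes and on an assumed sex split. The mismatch itself rests on neither. It should be fixed, but it does not touch the study's main sufentanil-versus-placebo result.

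**What to change.** Remove the sex item from the list of paired comparisons and say which analysis is meant.

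- **If a between-sex comparison is meant:** compute each participant's placebo-minus-sufentanil CSI difference and compare men with women by a Welch t-test, or by Mann-Whitney if clearly non-normal. Alternatively, test the trial-by-sex interaction in a mixed model; with complete data this matches the pooled-variance t-test rather than Welch. Report the number analysed per sex and the difference with its 95% CI. Do not read a non-significant result as showing that the sexes respond alike.
- **If only the drug effect within each sex is meant:** say so, keep the paired tests, state whether they are one- or two-sided, and draw no between-sex conclusion from them.
- **If an unpaired test was already used:** name it.

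The cost is one sentence of wording and, if a between-sex test is wanted and was not done, one re-run on existing data. No new data are needed.

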Less likely These risks are expected to occur in 5-20 subjects or less out of 100 subjects.	
 • N/A 	
 • N/A
Rare These risks are expected to occur in less than 5 subjects out of 100		
 • N/A

Form A

STU-2021-0579

		
4.d. List ALL other research procedures or components not listed in table 4.b. The combination of Tables 4b and 4d should account for all of the research procedures that will take place during this study.
 
Consider grouping similar procedures under a single component (e.g., blood work, CT = safety assessments)
		
#	Research component 
individual procedures example: Eligibility Assessments 
History and physicalQuestionnaireLaboratory tests Add or delete rows as needed	Column A Local Standard Practice Indicate the number of times each procedure will be performed as stipulated in the research plan that would be performed if the participant were not participating in the study.	Column B Research Only Indicate the number of times each procedure will be performed solely for research purposes (meaning that the participant would not undergo the same number of procedures or would not undergo the procedure(s) at the same frequency if they were not participating in the study)	Column D Risks If you are requesting a Waiver of Informed Consent, complete the table below. List the reasonably expected risks for each procedure or group of procedures under the following categories as appropriate: 
• Serious and likely;• Serious and less likely;• Serious and rare;• Not serious and likely;• Not serious and less likely
1	Eligibility assessments			
	Body height and mass, waist and hip circumference	0	Body height = 1, body mass recorded at each visit, waist and hip circumference = 1	
	Heart rate and rhythm via 12-lead ECG	0	1	
	Brachial blood pressure	0	Usually 3 to 5 measures	
2	Other assessments			
	Health history assessment	0	1	
	Lower-body negative pressure tolerance assessment	0	2	
3	Blood sampling			
	Blood sampling	0	Up to 10 draws (up to 5 draws per visit; baseline, and up to 4 time points post-drug/placebo administration). Total blood withdrawn: ~8 tablespoons.	

Form A

STU-2021-0579

4	Cardiovascular and other physiological measures			
	Heart rate and rhythm via ECG	0	continuous throughout visits	

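### The baseline versus post-drug by condition comparison planned in section 4.a is not specified in the Statistical Analysis section, whose two-way models carry no pre-drug information

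*Combined protocol and SAP*

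**What the plan says.** Section 4.a states that at the experimental visits "we will record baseline cardiovascular measures", and that in the analysis "we will compare cardiovascular data (inclusive of nervous system activity data) between time points (baseline and post-drug/placebo administration) and conditions". It adds: "All data will be analyzed while blind to condition and with proper co-variate analysis". No covariate is named there or elsewhere. On pain testing the same section says that "both before and after sufentanil/placebo administration, pain perception will be accessed via a cold pressor test" and pressure algometry. With two visits, that makes four cold pressor tests per participant. The blood sampling row of table 4.d gives "up to 5 draws per visit; baseline, and up to 4 time points post-drug/placebo administration".

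The Statistical Analysis section at the end of the document gives two models for these responses. The first reads "Cardiovascular and cerebrovascular responses were evaluated every 30 seconds for the cold pressor test [time x trial" (bracket closed in the source); the second reads "and the last minute of each LBNP stage [LBNP stage x trial" (likewise). Both are fitted as two-way repeated-measures ANOVA or a mixed-effects model, with Šidák comparisons only after a significant interaction. Paired t or Wilcoxon tests cover paired data generally. The examples given are urine specific gravity, CSI, pain ratings and sex differences in CSI, and the list is left open. Catecholamines are compared between trials by a mixed-effects model. Nerve activity does not appear in this section.

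**The concern.** A shift in resting pressure, heart rate, cerebral velocity or nerve activity after dosing, before any suction is applied, is a natural first explanation for a change in LBNP tolerance. Section 4.a plans the comparison that would show it. The Statistical Analysis section has no model in which that comparison can be recognised.

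There is also a question of precision. The two trials take place on different days. If stage or time values are compared between days without reference to that day's pre-drug value, ordinary day-to-day variation and re-sited sensors add noise to the drug contrast. Nerve recordings are the clearest case. Section 5.a rules out recording from the same nerve twice within 28 days, and the document states no interval between visits, so the two recordings may come from different nerves. The same visit's pre-drug recording is then the obvious reference, and table 4.d has the electrode in place from the start of the visit.

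**Working it through.** **1. The plan's own figure.** The plan gives no figure on this point. Its one calculation is the sample size of 15 for CSI. The SD of the paired difference is sqrt(402² + 300² − 2 × 0.5 × 402 × 300) = 361.9, and (988 − 741)/361.9 = 0.68, as stated. At power 0.80 and alpha 0.05 a paired t-test needs 15 participants one-sided (19 two-sided), so the figure reproduces one-sided. With the 29 recruited, two-sided power for an effect size of 0.68 is 0.94. None of this bears on the gap described here.

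**2. The two sections side by side.**

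| Item | Section 4.a | Statistical Analysis section |
|---|---|---|
| Pre/post-drug contrast by condition | Planned | Not stated |
| Nerve activity | Included | Not named |
| Covariates | Promised, not named | None |
| Cold pressor tests | Before and after dosing, each visit | One time by trial model; which test is not stated |
| LBNP stages | Not described here | Stage by trial; whether rest is a stage is not stated |

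Section 5.a starts LBNP at 40 mmHg and describes no 0 mmHg stage. Even if a resting stage were included, a uniform drug shift at rest and at every stage produces no interaction. The Šidák step would not be reached, and the resting difference would be absorbed into an overall trial effect.

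**3. What the pre-drug value could add.** For each participant let D_post be the sufentanil minus placebo difference in the outcome, and D_pre the same visit difference in the pre-drug value. D_pre precedes dosing, so the drug cannot have caused it. Regress D_post on D_pre: the intercept is the adjusted drug effect. With rho the correlation of D_post and D_pre, residual variance is multiplied by 1 − rho².

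Small-sample cost at n = 29: estimating the slope inflates the standard error by about sqrt(1 + 1/26) = 1.019, and the t quantile moves from 2.048 (28 df) to 2.052 (27 df), a factor of 1.002. Together these give about 1.02.

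Width ratio ≈ 1.02 × sqrt(1 − rho²):

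| rho (assumed) | sqrt(1 − rho²) | CI width ratio |
|---|---|---|
| 0 | 1.000 | 1.02 |
| 0.2 | 0.980 | 1.00 |
| 0.3 | 0.954 | 0.97 |
| 0.5 | 0.866 | 0.88 |
| 0.7 | 0.714 | 0.73 |

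Simulating the same contrast gives 1.02, 0.998, 0.974, 0.884 and 0.729. Break-even is near rho = 0.2.

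**4. Covariate or change score.** Suppose a share v of within-subject variance is common to a visit; then rho = v. The post-minus-pre by trial contrast has variance 2(1 − v) relative to a post-only contrast: 2.0 at v = 0, 1.0 at 0.5, 0.5 at 0.75, 0.2 at 0.9. It loses precision below v = 0.5. The covariate factor 1 − v² is never larger, because 2(1 − v) − (1 − v²) = (1 − v)².

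**The case against.** A reader might infer that the drug's resting effect is untested, that pre-drug data go unused, or that the cold pressor effect is halved because pre- and post-drug tests are averaged under one trial label. The documents support none of these.

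- The paired-test sentence is open-ended, and a resting sufentanil-placebo comparison is a paired comparison. Its examples include no cardiovascular or nerve variable, so coverage is possible but not stated.
- Pain ratings, taken before and after dosing, and catecholamines, with a baseline draw, are both analysed. Their pre-drug values may well be used.
- The time by trial model could be fitted separately to the pre-drug and post-drug cold pressor tests, which neither dilutes nor discards anything. Nothing in the document describes pooling.
- The text does not say whether responses are absolute values or changes from baseline, so the added noise between days is a possibility, not a documented fact.
- Section 4.a promises covariate analysis and refers to companion studies that are not in the document. That may be where the detail lies, but no covariate is named here.

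Two further objections concern the remedy. First, using the pre-drug data may cost precision. That holds for change scores when v is below 0.5; it does not carry over to covariate adjustment, whose worst case at n = 29 is about 2%. Second, the benefit rests on an assumed rho and was worked out for a single paired contrast. This stands. The LBNP model has several stages, participants leave it as they reach pre-syncope, and one resting correlation need not hold at every stage. The post-drug cold pressor test follows LBNP, which may weaken its correlation with the pre-drug test.

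Finally, the Statistical Analysis section is in the past tense, so new models may be post hoc. That is a reason to label them, not to omit them.

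**Conclusion.** The point holds as a gap in specification with a cheap improvement attached. The planned baseline versus post-drug by condition comparison is not specified; the two stated models have no pre/post-drug term or baseline covariate; nerve activity is not named; and the reader cannot tell which cold pressor test is modelled or whether stage includes rest. The most that can be said of the resting effect is that it is unclear whether and how it was analysed.

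The size of the gain depends on a correlation the documents do not give. It runs from a loss of about 2% in interval width at rho 0, through no change near 0.2, to intervals about 12% narrower at 0.5 and 27% narrower at 0.7. These figures assume 29 complete pairs and a single contrast. The CSI comparison between trials, which answers the study's objective, is untouched. The matter is worth correcting because it affects the mechanistic explanation of the result, but it does not threaten the main conclusion.

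**What to change.** Reconcile section 4.a with the Statistical Analysis section, and specify:

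1. For each resting variable, nerve activity included, the post-drug, pre-LBNP sufentanil-placebo difference adjusted for the between-visit difference in pre-drug value, with a 95% confidence interval. A regression of D_post on D_pre is enough.
2. In the LBNP stage by trial model, the same visit's pre-drug resting value as a covariate, entered as the within-subject visit difference so that differences between people do not drive the slope. State whether rest is a stage.
3. For the cold pressor test, a model of the post-drug test with the same visit's pre-drug test as covariate. State how the pre-drug tests are otherwise reported.

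Sections 4.a and 4.d indicate that the values are already collected, so the cost is wording and modest programming. Statistically it is about one degree of freedom per model and, with all 29 pairs, intervals up to about 2% wider if rho is near 0. If the adjusted models are added after unblinding, label them post hoc and show the stated models beside them.
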